9.1 Definitions

9.1.1 Adverse Event

As per the ICH guidelines, an AE is any untoward medical occurrence in a patient or clinical investigation subject administered a pharmaceutical product and which does not necessarily have a causal relationship with this treatment. An AE can, therefore, be any unfavorable and unintended sign (including an abnormal, clinically significant laboratory finding), symptom, or disease temporally associated with the use of a medicinal (investigational) product, whether or not considered related to the medicinal (investigational) product.

The period of observation for AEs extends from the time the subject gives informed consent until the End of Study (see [Section 9.4](#) for further details).

AEs may include:

- Exacerbation (ie, an increase in the frequency or severity) of a pre-existing condition. Illness present before study entry should be recorded in the medical history section of the

eCRF and only be reported as an AE if there is an increase in the frequency or severity of the condition during the study.

- A clinical event occurring after consent but before rVIII-SingleChain administration.
- Intercurrent illnesses with an onset after administration of rVIII-SingleChain.

AEs do not include:

- Events identified at screening that meet exclusion criteria.
- Medical procedures (the condition that leads to the procedure is the AE).
- Situations where an untoward medical occurrence has not taken place. For example:
 - Planned hospitalizations due to pre-existing conditions, which have not worsened.
 - Hospitalizations that occur for procedures not due to an AE (eg, cosmetic surgery).
 - Hospitalizations for a diagnostic procedure where the hospital stay is less than 24 hours in duration or for normal management procedures (eg, chemotherapy).
- Overdose of rVIII-SingleChain or any concomitant therapy that does not result in any adverse signs or symptoms.
- Major or minor bleeding episodes that occur as a result of the subject's unchanged, pre-existing severe hemophilia A.

For laboratory safety parameters, any instances of absolute values being outside the reference range or changes at any visit after study start that are considered by the investigator as clinically significant must be recorded in the eCRF as AEs. In addition, at the investigator's discretion, any changes or trends over time in laboratory parameters can be recorded in the eCRF as AEs if such changes or trends are considered to be clinically relevant, even if the absolute values are within the reference range.

Laboratory findings do not need to be reported as AEs in the following cases:

- Laboratory parameters already beyond the reference range at screening, unless a further increase / decrease can be considered an exacerbation of a pre-existing condition.
- Abnormal laboratory parameters caused by mechanical or physical influences on the blood sample (eg, in vitro hemolysis) and flagged as such by the laboratory in the laboratory report.
- Abnormal parameters that are obviously biologically implausible (eg, values that are incompatible with life or outside the measuring range).
- An abnormal laboratory value that cannot be confirmed after repeat analysis, preferably in the same laboratory (ie, the previous result could be marked as not valid and should not necessarily be reported as an AE).

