3.6 Study Monitoring Procedures

3.6.1 Data and Safety Monitoring Board (Arm 2 [PUPs] Only)

An IDMC will be established to monitor the evolving risk-benefit profile of rVIII-SingleChain in the PUPs in Arm 2, including data from the surgery and CCI substudies. The IDMC will review the data from Arm 2 periodically as well as on an ad-hoc basis, and their recommendations will pertain to Arm 2 only. At any time after review of data of inhibitors or other relevant safety data, the IDMC can recommend to stop or pause Arm 2 of the study or the substudies.

The IDMC is an independent expert advisory group consisting of 3 medically qualified persons with appropriate expertise in subjects with haemophilia A, in the treatment with FVIII replacement therapy and / or evaluation of AEs and laboratory results relevant for detecting inhibitors or any possible safety issues; in addition, there will be 1 independent statistician.

The IDMC will receive reports on confirmed inhibitor formation (including narratives for SAEs) as well as predefined other safety data at the following timepoints:

- Approximately every 3 months for the first 12 months after the first PUP in Arm 2 received their first rVIII-SingleChain dose.
- Approximately every 6 months thereafter until the End of Study Visit for the last PUP in Arm 2.
- In the event that an inhibitor has been identified, a summary table and subject summary will be sent to the IDMC chair to decide if an ad-hoc meeting is required.

IDMC meetings are scheduled to occur approximately at the following time points:

- When the first PUP in Arm 2 has achieved 25 EDs.
- When the first 5 PUPs in Arm 2 have achieved a minimum of 25 EDs each.
- Every 3 months for the first 12 months and every 6 months thereafter.
- If required: ad-hoc meetings in the event that an inhibitor has been identified.
- If required: ad-hoc meetings in the event of a related SAE or related adverse event of special interest (AESI) in the CCI substudy.

Further details on the composition, responsibilities, meeting schedule, data for review, and recommendations of the IDMC are available in the IDMC Charter.

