8.3.2 Treatment Assessment Performed at Study Site

Major bleeding episodes are defined as bleeding episodes for which a subject is required to seek treatment at the hemophilia center from the treating physician for any episode that threatens the subject's life or a loss of limb. Examples of major bleeding episodes include intracranial hemorrhage, gastrointestinal bleeding, and severe bleeding. All other bleeding episodes will be classified as non-major unless the investigator assessment notes otherwise.

The following will be recorded in the eCRF following treatment of a bleeding episode by the investigator:

- Reason for use of rVIII-SingleChain and type of the bleeding episode (major or non-major, traumatic or non-traumatic).
- Location of bleeding.

- Time of the start of bleeding.
- Dose of rVIII-SingleChain (IU/kg).
- Number of used vials and total actual IU infused.
- Date and start time of each injection.
- Concomitant therapy and other hemostatic product usage (if any).
- Efficacy evaluation by the investigator.
- AEs.
- Arms 2 and 3 only: investigator assessment of local tolerability if rVIII-SingleChain administered at the clinic.

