9.1.3 Serious Adverse Event

An SAE is defined as any untoward medical occurrence that at any dose:

- **Results in death** – The event must be the cause of death for the SAE to meet this serious criterion.
- **Is life-threatening** – The term “life-threatening” refers to an event in which the subject was at risk of death at the time of the event; it does not refer to an event that hypothetically might have caused death if it had been more severe.
- **Requires in-patient hospitalization or prolongation of existing hospitalization** – CSL considers “hospitalization or prolongation of existing hospitalization” for at least 24 hours as the defining criterion for an SAE. Hospital admissions for planned surgery or for normal disease management procedures (eg, chemotherapy) are not considered as defining criteria for SAEs.
- **Results in persistent or significant disability or incapacity.**
- **Is a congenital anomaly or birth defect.**
- **Is medically significant** – A medically significant event is defined as an event that does not necessarily meet any of the SAE criteria, but which is judged by a physician to potentially jeopardize the subject or require medical or surgical intervention to prevent one of the above outcomes listed as an SAE criterion.

AEs that do not fall into the above categories are defined as nonserious AEs.

All low-titer and high-titer inhibitors confirmed by the central laboratory are defined as SAEs (SAE criterion: “medically significant”) and must be reported and followed up accordingly.

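### The AE definition excludes major bleeds from unchanged hemophilia A with no exception for seriousness, so it is unclear whether a fatal or life-threatening bleed must be reported as an SAE

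*Protocol*

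**What the plan says.** - **Protocol 9.1.1 (Adverse Event)** has a list of what AEs do not include. One entry is "Major or minor bleeding episodes that occur as a result of the subject's unchanged, pre-existing severe hemophilia A". It carries no condition about seriousness. A separate list in the same section gives, among possible AEs, "Exacerbation (ie, an increase in the frequency or severity) of a pre-existing condition".
- **Protocol 8.3.2** defines a major bleed as one for which the subject must seek treatment at the hemophilia center for "any episode that threatens the subject's life or a loss of limb". It adds: "Examples of major bleeding episodes include intracranial hemorrhage, gastrointestinal bleeding, and severe bleeding".
- **Protocol 9.1.3** opens: "An SAE is defined as any untoward medical occurrence that at any dose", and then lists the seriousness criteria. For death it says: "The event must be the cause of death for the SAE to meet this serious criterion". Life-threatening refers to "an event in which the subject was at risk of death at the time of the event". There is no exception for bleeding.
- **Protocol 9.6** requires every SAE to reach the sponsor within 24 hours, whether or not it is causally related, and has it entered on the AE page of the eCRF.
- **Protocol 3.6.1** gives the IDMC for Arm 2 "reports on confirmed inhibitor formation (including narratives for SAEs) as well as predefined other safety data", and leaves the details to the IDMC Charter.
- **SAP 4.7.2** does not repeat the bleeding exclusion. It plans SAE tables and separate listings of SAEs and deaths.

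**The concern.** One section names major bleeds as outside the AE definition. Another defines that same class by a property that, at least for threat to life, is an SAE criterion. A site that meets an intracranial hemorrhage in a subject with no known inhibitor therefore has two instructions and no rule for choosing between them.

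For a replacement factor, a life-threatening bleed on treatment is a central harm from lack of effect. Section 8.6.1 itself gives lack of efficacy as a reason to suspect an inhibitor. After 25 EDs, PUPs on prophylaxis have scheduled visits and inhibitor samples only every 3 months, so such a bleed can come before the next planned test. If sites classify the same kind of bleed differently, the SAE incidence partly reflects local reading of the protocol, and some events lose the 24-hour reporting clock.

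**Working it through.** The plan gives no figure to reproduce. The check sets the sections side by side.

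**1. Is the excluded class serious by the protocol's own terms?** Largely, but not wholly.
- A bleed that threatens life (8.3.2) corresponds closely to the life-threatening criterion in 9.1.3, which asks for actual risk of death at the time. A fatal bleed meets the death criterion.
- A bleed that threatens only a limb needs a physician's judgment under the medically significant criterion, unless it also leads to disability or a hospital stay of at least 24 hours.

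**2. Does 9.1.3 settle the matter?** No.
- Its opening refers to any untoward occurrence and has no bleeding exception. That favors SAE status.
- However, it ends by calling whatever meets no criterion a nonserious AE, and 9.6 places SAEs on the AE page. Both treat an SAE as an AE that is also serious. On that reading, an event ruled out by 9.1.1 never reaches the criteria of 9.1.3.
- No sentence gives either section precedence.

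**3. Does the qualifier *unchanged*, or the exacerbation entry, settle it?** No.
- *Unchanged* is not defined. Eligible subjects have FVIII activity below 1%, so without an inhibitor an investigator can reasonably attribute a bleed to unchanged disease.
- If every life-threatening bleed counted as an exacerbation, the word *major* in the exclusion would have little left to cover.
- Exacerbation needs a baseline. PUPs enter at their first bleed or in a non-bleeding state (3.1), so many have little or none.

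**4. Does another safety route catch these bleeds?** Only in part.
- The events of special interest in Protocol 9.1.2 and SAP 4.7.2.1 and 4.7.2.2 include neither bleeding nor lack of effect.
- Protocol 9.10 asks for details of major bleeds, but only in Arm 2 subjects with an inhibitor SAE and only for 28 days after the End of Study Visit.
- The eCRF bleed record (8.3.2) holds type, treatment and efficacy rating. It also has an item for AEs, but 9.1.1 decides what qualifies there. No 24-hour clock attaches to the bleed record itself.
- The SAP's deaths listing would show a fatal bleed. It would not show an intracranial hemorrhage that the subject survived.

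**5. Size.** The documents give no expected number of major bleeds, so the number of omitted SAEs cannot be derived. The effect of one omission can be shown, assuming the planned minimum numbers and a subject with no other SAE:
- Arm 2: 1/24 = 0.042, or 4.2 percentage points of SAE incidence.
- Arms 1 and 3: 1/200 = 0.005, or 0.5 percentage points.

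**The case against.** The strongest reply is that the text can be read consistently. The exclusion covers only bleeds from unchanged disease, and worsening is an AE in the same section. Section 9.1.3 has no bleeding exception, 9.6 applies regardless of causality, and the SAP does not repeat the exclusion. Keeping disease bleeds in the efficacy data is a recognizable design choice. Major bleeds are also not hidden: treatment success for them is a primary endpoint in PUPs, and missing ratings count as failures. Centrally confirmed inhibitors are SAEs by rule, and each identified inhibitor sends a summary to the IDMC chair.

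Much of this stands, and it rules out four stronger conclusions that a reader might draw:
- *All major bleeds are removed from AEs.* The exclusion is limited to unchanged disease.
- *A fatal or life-threatening bleed is never an SAE.* No section says so, and 9.1.3 read alone says the opposite.
- *Every major bleed is a missed SAE.* Threat to limb alone needs a judgment of medical significance, and 8.3.2 leaves the investigator some discretion over classification.
- *The IDMC receives no prompt report of these bleeds.* It receives predefined other safety data under a charter that is not supplied. Bleeds may be among them.

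The reply does not show which section governs when an investigator attributes a life-threatening bleed to unchanged disease. Efficacy records and a deaths listing do not replace SAE reporting of a survived event.

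**Conclusion.** The concern holds as a conflict between two stated rules. Section 9.1.1 excludes a class of bleeds that overlaps heavily with the SAE criteria of 9.1.3, and the protocol names no order of precedence. A site following 9.1.1 may leave a fatal or life-threatening bleed out of 24-hour reporting and the SAE tables. The clearest gap is a survived life-threatening bleed in a subject without a known inhibitor, because the deaths listing and the inhibitor rules do not reach it.

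This rests on two assumptions: that some sites read SAEs as a subset of AEs, which the wording permits, and that some attribute such bleeds to unchanged hemophilia. How many events this would affect is unknown and could be none. The point is worth correcting because it concerns serious events in a small arm and the correction is short.

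**What to change.** Reconcile Protocol 8.3.2, 9.1.1 and 9.1.3:
- **Protocol 9.1.1:** limit the exclusion to bleeding episodes that meet none of the seriousness criteria in 9.1.3. State that a bleed meeting any of them is reported as an SAE under 9.6 and is also recorded for efficacy. The meaning of *unchanged* then matters only for non-serious bleeds, which stay out of the AE tables as intended.
- **SAP 4.7.2:** show bleeding SAEs on a separate row of the SAE table, so that SAE incidence can be read with and without them.

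The cost is one sentence in the protocol, one table row, a few more SAE reports and a slightly higher SAE count. The bleeds are already recorded, so no new assessment is needed. SAP 4.1.2 says the PTP analysis is complete, so the change would mainly affect Arm 2.

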9.1.2 Events of Special Interest

Medical events of special interest include:

- Invasive procedures other than surgery.
- Hospital admission for less than 24 hours for events not considered as SAEs.
- Positive test result for inhibitors performed at local laboratory.

AEs of special interest include:

- Hypersensitivity reactions (including anaphylactic reactions).
- Thromboembolic events.
- Any AE related to rVIII-SingleChain associated with double or higher dose than prescribed.

9.1.3 Serious Adverse Event

An SAE is defined as any untoward medical occurrence that at any dose:

- **Results in death** – The event must be the cause of death for the SAE to meet this serious criterion.
- **Is life-threatening** – The term “life-threatening” refers to an event in which the subject was at risk of death at the time of the event; it does not refer to an event that hypothetically might have caused death if it had been more severe.
- **Requires in-patient hospitalization or prolongation of existing hospitalization** – CSL considers “hospitalization or prolongation of existing hospitalization” for at least 24 hours as the defining criterion for an SAE. Hospital admissions for planned surgery or for normal disease management procedures (eg, chemotherapy) are not considered as defining criteria for SAEs.
- **Results in persistent or significant disability or incapacity.**
- **Is a congenital anomaly or birth defect.**
- **Is medically significant** – A medically significant event is defined as an event that does not necessarily meet any of the SAE criteria, but which is judged by a physician to potentially jeopardize the subject or require medical or surgical intervention to prevent one of the above outcomes listed as an SAE criterion.

AEs that do not fall into the above categories are defined as nonserious AEs.

All low-titer and high-titer inhibitors confirmed by the central laboratory are defined as SAEs (SAE criterion: “medically significant”) and must be reported and followed up accordingly.

9.2 Severity of Adverse Events

The severity of each AE (ie, nonserious and serious AEs) is to be assessed by the investigator as follows:

Table 10: Severity of Adverse Events

Severity	Definition
Mild	A type of AE that is usually transient and may require only minimal treatment or therapeutic intervention. The event does not generally interfere with usual activities of daily living.
Moderate	A type of AE that is usually alleviated with additional specific therapeutic intervention. The event interferes with usual activities of daily living, causing discomfort but poses no significant or permanent risk of harm to the subject.
Severe	A type of AE that interrupts usual activities of daily living, or significantly affects clinical status, or may require intensive therapeutic intervention.

Abbreviations: AE = adverse event; CDISC = Clinical Data Interchange Standards Consortium; SDTM = Severity Intensity Scale for Adverse Event Terminology.

9.3 Causality of Adverse Events

The causal relationship of an AE to rVIII-SingleChain must always be assessed by the investigator. All AEs will be classified as either **related** or **not related** to rVIII-SingleChain. If a causality assessment is not provided for an AE (including an SAE), that AE will be considered related to rVIII-SingleChain.

The degree of certainty with which an AE is attributed to rVIII-SingleChain or an alternative cause (eg, natural history of the underlying disease, concomitant therapy) will be determined by how well the event can be understood in terms of:

- Known pharmacology of rVIII-SingleChain.
- Clinically and / or pathophysiologically plausible context.
- Reaction of a similar nature previously observed with similar products, or reported in the literature for similar products as being product related (eg, headache, facial flushing, pallor).
- Plausibility supported by the temporal relationship (eg, the event being related by time to administration or termination of treatment with rVIII-SingleChain, drug withdrawal or reproduced on rechallenge).

9.4 Observation Period for Adverse Events

The observation period for AE (and SAE) reporting in an individual subject will start at the time of giving written informed consent for participation in the current study and finish with the End of Study Visit.

If the investigator becomes aware of an SAE that has started after the observation period has finished, and the event could in some way be associated with rVIII-SingleChain (irrespective of whether or not it is considered by the investigator to be causally related to rVIII-SingleChain), then this must also be reported to CSL and included in the clinical database (see Section 9.6).

9.5 Adverse Event Reporting

9.5.1 Adverse Events

At each clinical evaluation, the investigator (or delegate) will determine whether any AEs have occurred. AEs will be recorded in the AE page of the eCRF. If known, the medical diagnosis of an AE should be recorded in preference to the listing of individual signs and symptoms. The investigator must follow up on the course of an AE until resolution or stabilization. If an AE is ongoing after the End of Study Visit, the AE will continue to be followed up until resolution, stabilization, or 28 days after the final administration of rVIII-SingleChain, whichever is sooner. Inhibitor SAEs in Arm 2 (PUPs) will be followed up for 28 days after the End of Study Visit (see [Section 9.10](#)).

If, during the study period, a subject presents with a preexisting condition that was not noted at the time of study entry, the condition should be retrospectively recorded in the Medical History section of the eCRF.

9.5.2 Events of Special Interest Reporting

Any AE of special interest or medical event of special interest will be recorded in the eCRF and will be automatically reported to the sponsor via email alert.

9.6 Serious Adverse Event Reporting

This study will comply with all applicable regulatory requirements and adhere to the full requirements of ICH Topic E2A (Clinical Safety Data Management: Definitions and Standards for Expedited Reporting).

For SAEs occurring during the study, the investigator or delegate will enter all relevant information in the AE page of the eCRF. An electronic document containing the AE page and other applicable pages of the eCRF must be sent (via facsimile or email) to the sponsor together with a **Notification of Serious Adverse Event at Investigator Site** cover page, which has been signed and dated by the investigator. If an electronic document is not able to be generated (eg, internet access problem), a handwritten paper SAE report must be completed, which must be signed and dated by the investigator.

All SAEs that occur during the course of the study, whether or not causally related to rVIII-SingleChain, must be reported immediately (within 24 hours of the investigator becoming aware of the event) to CSL. For Japan sites only, the investigator must also inform the head of the medical institution of the SAE and related information in accordance with the Japanese regulatory requirements and ICH GCP.

AEs occurring in the period between the times the subject gave written informed consent and the first exposure to rVIII-SingleChain that meet one or more of the seriousness criteria for AEs must be reported to CSL in the same manner as other SAEs and will be included in the clinical study database.

Any SAE that occurs after the End of Study Visit that is considered to be causally related to rVIII-SingleChain must be **reported immediately (ie, within 24 hours of the investigator becoming aware of the event) to CSL.** For Japan sites only, the investigator must also inform the head of the medical institution of the SAE and related information in accordance with the Japanese regulatory requirements and ICH GCP.

Contact details and guidance for reporting SAEs will be provided to study site before the study site is initiated.

